Part C1, dose escalation/de-escalation using the mTPI-2 design with an every 14-day dosing regimen, will enroll up to 24 subjects (3 to 6 subjects at each dose level) for the purposes of MTD/RP2D decisions.

Part C2, with an every 14-day dosing regimen, is designed to provide a preliminary assessment of clinical activity at the MTD/RP2D. Once the MTD/RP2D is defined in Part C1, expansion cohorts of up to 40 subjects in selected tumor types will be enrolled as described in Part B to evaluate the antitumor activity using the MTD/RP2D in Part C2. A 2-stage design may be incorporated into this cohort.

Part D1, dose escalation/de-escalation using the mTPI-2 design for CX-2009 with an every 14-day dosing regimen in combination with CX-072, will enroll up to 24 subjects (3 to 6 subjects at each dose level) for the purposes of MTD/RP2D decisions.

Part D2, dose expansion of CX-2009 plus CX-072 with an every 14-day dosing regimen, is designed to provide a preliminary assessment of clinical activity at the MTD/RP2D. Once the MTD/RP2D is defined in Part D1, expansion cohorts of 40 subjects in selected tumor types will be enrolled as described in Part B to evaluate the antitumor activity of CX-2009 plus CX-072. A 2-stage design may be incorporated into this cohort.

Part E1, dose escalation using the mTPI-2 design for CX-2009 with an every 21-day dosing regimen in combination with CX-072, will enroll up to 24 subjects (3 to 6 subjects at each dose level) for the purposes of MTD/RP2D decisions.

Part E2, dose expansion of CX-2009 plus CX-072 with an every 21-day dosing regimen, is designed to provide a preliminary assessment of clinical activity at the MTD/RP2D. Once the MTD/RP2D is defined in Part E1, expansion cohorts of 40 subjects in selected tumor types will be enrolled as described in Part B to evaluate the antitumor activity of CX-2009 plus CX-072. A 2-stage design may be incorporated into this cohort.

Enrollment within the expansions will be suspended if either of the following Safety Stopping Rules are met in the first 6 subjects enrolled in Parts B, C2, D2, and E2:

- DLT rate is >30% within 21 days (Parts B and E2) or within 28 days (Parts C2 and D2) of the first dose of study drug
- >20% of subjects have a treatment interruption or discontinuation within the first 6 weeks of the first dose of study drug or within 6 weeks of a single dose reduction step for subjects who experience events with their first dose of study drug

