Part C1 initiated at a dose level of 6 mg/kg every 14 days, AIBW (selected from among the following indications: BC, NSCLC, or HNSCC). Prior to a dose escalation/de-escalation, a minimum of 3 evaluable subjects must be assessed ([Figure 6](#)). Subsequent dose escalation/de-escalation (if any) will be based upon the observed safety tolerability profile as determined in consultation with the SRC.

Part C1 will evaluate dose levels based on DLT events and TRAEs leading to treatment delay or discontinuation, including events of special interest (eg, ocular toxicity and peripheral neuropathy).

AEs that meet DLT criteria (within the 28-day DLT period) and delayed AEs that lead to treatment interruption/discontinuation within the first 6 weeks, thus encompassing the first 3 doses (DLT rate $\leq 30.0\%$; delayed AE rate $\leq 20.0\%$), will be monitored. Decision for dose escalation/de-escalation will be made by the Sponsor in consultation with the SRC guided by the decision-making table ([Appendix C](#)). The selection of MTD/RP2D with an every 14-day dosing regimen will be based predominantly on safety and may take other factors into account such as PK/PD and clinical activity.

Subjects who discontinue study drug administration for reasons other than DLTs may be replaced to ensure the minimum number of subjects required for DLT evaluation is enrolled.

3.7 Part C2 (CX-2009 Monotherapy): Dose Expansion at the MTD/RP2D for Every 14-Day Dosing Regimen in Selected Tumor Types (Maximum n ≤ 200)

To explore efficacy of CX-2009 for every 14-day dosing regimen, indication-specific expansion cohorts will be opened to obtain preliminary evidence of clinical activity. Part C2 will enroll up to a total of 40 subjects each in 1 or more of the tumor types listed in [Table 4](#). These tumor types have been selected for their responsiveness to MTIs and general availability of lesion safe to be biopsied. Part C2 may be initiated as soon as the MTD/RP2D for the 14-day regimen is defined in consultation with the SRC and will only be initiated if, after the review of dose escalation data (Part C1), an every 14-day dosing regimen is considered for further development.

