Allocation of Subjects Between Parts C, D, and E. In case Parts C, D, and E are open for enrollment concurrently and subjects meet the eligibility criteria for all parts, the Sponsor in conjunction with the Principal Investigator will determine to which part the subjects are allocated. The Sponsor will determine which tumor types will be selected for additional evaluation for Parts B, C2, D2, and E2.

Note: Dose expansion for CX-2009 monotherapy may occur under the every 21-day dosing regimen (Part B) and/or the every 14-day dosing regimen (Part C2), depending on available data from Parts A, A2, and C1. Selection of the regimen for dose expansion will be made in consultation with the SRC.

3.8 Part D1 (CX-2009 + CX-072): Dose Escalation/De-escalation and Determination of MTD/RP2D for Every 14-Day Dosing Regimen in Selected Tumor Types (n ≤ 24)

Part D1 is only open to those countries in which the Health Authority permits the combination of CX-2009 and CX-072 to be investigated. The dose of CX-072 will be fixed at the RP2D (800 mg every 14 days). The starting dose for CX-2009 will be set at the every 14-day monotherapy RP2D as determined in Part C1. Lower starting doses may be used based on emerging safety data and in consultation with the SRC. The mTPI-2 design will be used to determine the MTD/RP2D for this schedule. The following cohort's dose will be increased or decreased according to the defined dose escalation rules based upon the observed safety tolerability profile as determined in consultation with the SRC. Prior to a dose escalation/de-escalation, a minimum of 3 evaluable subjects must be assessed per the mTPI-2 algorithm ([Figure 6](#)). Part D1 will enroll subjects in 1 or more of the tumor types listed in [Table 4](#). The tumor types have been selected for their responsiveness to MTIs and general availability of lesion safe to be biopsied.

Part D1 will evaluate dose levels based on DLT events and TRAEs leading to treatment delay or discontinuation, including events of special interest (eg, ocular toxicity and peripheral neuropathy).

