Both mTPI and mTPI-2 designs are transparent and user-friendly to both statisticians and clinicians, as all the decisions can be tabulated for examination prior to the trial. Figure 6 and Figure 7 are dose-finding decision tables for up to 14 subjects with target toxicity probability of 30.0% and 20.0%, respectively. In these tables, the columns represent the number of subjects treated at the current dose and rows denote the number of subjects experiencing DLT at that dose. The table enumerates all the possible dose-finding decisions, and therefore can be used to design and conduct the trial conveniently.

Figure 6. Decision Table for mTPI-2 Cohort (Target Toxicity Probability = 30.0%)

		Number of Patients													
		1	2	3	4	5	6	7	8	9	10	11	12	13	14
Number of Patients with DLTs	0	E	E	E	E	E	E	E	E	E	E	E	E	E	E
	1	D	D	S	S	E	E	E	E	E	E	E	E	E	E
	2		D	D	D	D	S	S	S	E	E	E	E	E	E
	3			DU	DU	D	D	D	D	S	S	S	S	E	E
	4				DU	DU	DU	D	D	D	D	D	S	S	S
	5					DU	DU	DU	DU	DU	D	D	D	D	D
	6						DU	DU	DU	DU	DU	DU	D	D	D
	7							DU	D						
	8								DU						
	9									DU	DU	DU	DU	DU	DU
	10										DU	DU	DU	DU	DU
	11											DU	DU	DU	DU
	12												DU	DU	DU
	13													DU	DU
	14														DU

A decision table of the mTPI-2 design, with 14 subjects, the target probability of $p_T = 0.3$ and 2 values $\epsilon_1 = \epsilon_2 = 0.05$.

D = de-escalate to a lower dose; DLT = dose-limiting toxicity; DU = de-escalate to a lower dose and the current dose will never be used again in the study; E = escalate to the next higher dose; mTPI-2 = modified toxicity probability interval 2; S = stay at the same dose.

Figure 7. Decision Table for mTPI-2 Cohort (Target Toxicity Probability = 20.0%)

		Number of Patients													
		1	2	3	4	5	6	7	8	9	10	11	12	13	14
Number of Patients with DLTs	0	E	E	E	E	E	E	E	E	E	E	E	E	E	E
	1	D	D	D	D	S	S	S	E	E	E	E	E	E	E
	2		DU*	DU	D	D	D	D	D	S	S	S	S	S	S
	3			DU	DU	DU	DU	D	D	D	D	D	D	S	S
	4				DU	DU	DU	DU	DU	DU	D	D	D	D	D
	5					DU	D								
	6						DU								
	7							DU							
	8								DU						
	9									DU	DU	DU	DU	DU	DU
	10										DU	DU	DU	DU	DU
	11											DU	DU	DU	DU
	12												DU	DU	DU
	13													DU	DU
	14														DU

$n = 14, p_T = 0.2, \epsilon_1 = 0.05, \epsilon_2 = 0.05$

A decision table of the mTPI-2 design, with 14 subjects, the target probability of $p_T = 0.2$ and 2 values $\epsilon_1 = \epsilon_2 = 0.05$.

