D = de-escalate to a lower dose; DLT = dose-limiting toxicity; DU = de-escalate to a lower dose and the current dose will never be used again in the study; E = escalate to the next higher dose; mTPI-2 = modified toxicity probability interval 2; S = stay at the same dose.

*: If at the first dose level, users can choose to early-terminate the study or not based on their own discretion.

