Appendix E: Safety Review Committee

A Safety Review Committee (SRC) has been established for the study. The SRC will consist of selected Investigators from the trial and representatives from CytomX Therapeutics, Inc. who will review on a regular basis, the cumulative safety data from each cohort in the study in order to:

- Approve dose escalation to the next cohort in Part A of the study;
- Recommend modifications to the dose or schedule as it pertains to subject safety; or
- Recommend modifications to the Module related to subject oversight (eg, additional safety monitoring, changes to inclusion/exclusion criteria).

Actions taken regarding dose escalation or amendments to the Module will be documented and stored in the trial master file for the study.

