Part B: Dose expansion (proof of concept) at the MTD/RP2D of CX-2009 monotherapy every 21-day dosing regimen with proof of concept in selected tumor types (maximum $n \leq 200$): This part will explore efficacy of CX-2009 by requiring measurable disease and selecting for confirmed high CD166 expressing tumors. Part B will enroll up to a total of 40 subjects in each of 1 or more of the 5 tumor types listed in Table 4 in the CTMX-M-2009-001 Protocol Module. Part B will only be initiated if, after the review of dose escalation data (Parts A and A2), an every 21-day dosing regimen is considered for further development.

Part C1: Dose escalation and determination of the MTD/RP2D of the CX-2009 monotherapy every 14-day dosing regimen in subjects with high CD166 expression ($n \leq 18$): The highest dose level tested in this clinical study for CX-2009 was 10 mg/kg administered every 21 days, which successfully cleared the DLT evaluation period. The every 14-day dosing regimen equivalent of 10 mg/kg administered every 21 days is ≥ 7 mg/kg. In order to provide an additional margin of safety coverage for Part C1, the starting dose will be 6 mg/kg, AIBW, administered every 14 days. The mTPI-2 design will be used to determine the MTD/RP2D for this schedule. The following cohort's dose will be increased according to the defined dose escalation

rules to 8 mg/kg and then to 10 mg/kg based upon the observed safety tolerability profile as determined in consultation with the SRC. Prior to a dose escalation, a minimum of 3 evaluable subjects must be assessed per the mTPI-2 algorithm (Figure 6 from the CTMX-M-2009-001 Protocol Module). The maximum dose level that will be tested in Part C1 will be 10 mg/kg. Part C1 will include up to 18 subjects. Subjects will be selected from the following indications: BC, NSCLC, or HNSCC.

Figure 1: Study Design Schema: Parts A, A2, and B (every 21-day Dosing Regimen)

^a Part A eligible tumor types: BC, CRPC, NSCLC, OEC, EC, HNSCC, and CCC.

^b Part A2 restricted to subjects with BC, NSCLC, OEC, EC, and HNSCC.

[figure not shown]
^c Part A mTPI-2 cohort eligible tumor types: BC, NSCLC, and HNSCC.

^d Part B eligible tumor types: TNBC, HR-positive/HER2-negative BC, NSCLC, OEC, and HNSCC.

Note: Parts A (mTPI-2 cohort only), A2, and B will enroll subjects with confirmed high CD166 expressing tumors.

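### In Parts C1, D1 and E1 the three-evaluable-subject minimum also covers de-escalation and has no express exception when both of the first two subjects have events in the same decision table, which already says to go down

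*Protocol*

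**What the plan says.** **The minimum.** Module Section 3.6 (Part C1) states: "Prior to a dose escalation/de-escalation, a minimum of 3 evaluable subjects must be assessed", with a reference to Figure 6. Sections 3.8 (D1) and 3.10 (E1) state: "Prior to a dose escalation/de-escalation, a minimum of 3 evaluable subjects must be assessed per the mTPI-2 algorithm", again citing Figure 6. Section 3.1 and the synopsis repeat both forms.

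**Cohort size.** For each of the three parts, Section 9 says it "will enroll up to 24 subjects (3 to 6 subjects at each dose level) for the purposes of MTD/RP2D decisions".

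**Events and tables.** Sections 3.6, 3.8 and 3.10 monitor DLTs against 30% and delayed adverse events against 20%. Appendix C gives one decision table for each target: Figure 6 for 30% and Figure 7 for 20%. DU means "de-escalate to a lower dose and the current dose will never be used again in the study". The DU at 2 of 2 in Figure 7 has a footnote: "If at the first dose level, users can choose to early-terminate the study or not based on their own discretion".

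**Replacement.** Subjects who stop study drug for reasons other than DLTs "may be replaced to ensure the minimum number of subjects required for DLT evaluation is enrolled".

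**Safety Review Committee (SRC).** Under Appendix E the SRC may "Recommend modifications to the dose or schedule as it pertains to subject safety".

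**SAP.** Section 4.1, written on Module Amendment 06, words the C1 rule as: "Prior to a dose escalation, a minimum of 3 evaluable subjects must be assessed per the mTPI-2 algorithm".

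**The concern.** A minimum cohort size before escalation protects subjects, because it stops the dose rising on thin evidence. The same minimum before de-escalation works the other way. If the first two evaluable subjects both have qualifying events, the table has already answered. The written rule nevertheless asks for a third assessed subject before the cohort may move down.

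What is at stake is one further subject treated at a dose the table says to leave, or a cohort held with no stated route to the lower dose. The drug produced Grade 3 neuropathy in one subject and Grade 3 transaminase elevations in another among five evaluable subjects at 6 mg/kg every 14 days (Section 5.2.1.1).

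**Working it through.** **1. The printed cells (Appendix C).** E = escalate, S = stay, D = de-escalate, DU = de-escalate and close the dose.

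| Events / evaluable | Figure 6 (30%) | Figure 7 (20%) |
|---|---|---|
| 1/1 | D | D |
| 1/2 | D | D |
| 2/2 | D | DU* |
| 1/3 | S | D |
| 2/3 | D | DU |
| 3/3 | DU | DU |

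**2. Reproducing the tables.** I used mTPI-2 with half-widths of 0.05 (Appendix C) and two assumptions the documents do not state: a Beta(1,1) prior, and DU when P(rate > target) exceeds 0.95. This matched 90 of 91 cells compared in Figure 6 and 73 of 74 in Figure 7. The three-subject cells all match:

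- 30% target, 2/3: posterior Beta(3,2); P(rate > 0.3) = 0.2401 + 0.4116 + 0.2646 = 0.916, so D.
- 30% target, 3/3: 1 − 0.3⁴ = 0.992, so DU.
- 20% target, 2/3: 0.4096 + 0.4096 + 0.1536 = 0.973, so DU.
- 20% target, 3/3: 1 − 0.2⁴ = 0.998, so DU.

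The two mismatches are 2/2 in Figure 6 (printed D; 1 − 0.3³ = 0.973 would give DU) and 1/1 in Figure 7 (printed D; 1 − 0.2² = 0.960 would give DU). Both still point down.

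**3. Two of two in the same table.** A third subject leads to 2/3 or 3/3. In Figure 6 that is D or DU; in Figure 7 it is DU either way. Neither S nor E can be reached. The third result settles only D versus DU, and only in Figure 6.

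**4. Where the argument stops.**

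- *Single event.* After 1/1 or 1/2, a cohort of three with no further event gives 1/3 = S in Figure 6, so completing it is informative. In Figure 7, 1/3 is still D. I leave that case out because the sentence cites Figure 6, one event is thin evidence, and the same table prints S at 1/5.
- *Different tables.* One DLT plus one delayed event, counted separately, can give 1/3 = S in Figure 6. Two delayed events that are not DLTs can give 0/3 = E or 1/3 = S there. The Module does not say for C1, D1 or E1 how the two tables combine.

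**5. How often.** If the first two subjects are read before a third is treated, the chance is p²: 0.3² = 9% at a 30% event rate and 0.4² = 16% at 40%. That overstates it when cohorts are filled together. For n enrolled, exactly two evaluable and both with events, the chance is

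C(n,2) × (1 − q)² × qⁿ⁻² × p².

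Take q = 1/6 (six enrolled and five evaluable at 6 mg/kg every 14 days, Section 5.2.1.1) and p = 2/5 from the same cohort:

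- n = 3: 3 × 0.6944 × 0.1667 × 0.16 = 5.6%
- n = 4: 1.9%
- n = 5: 0.5%
- n = 6: 0.13%

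The exact 95% interval for 1/6 is 0.4% to 64%. Over that range the n = 3 figure runs from 0.2% to 7.1%, with its maximum at q = 1/3. These are illustrations, not estimates.

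**The case against.** **General latitude.** Decisions are made by the sponsor with the SRC and are only guided by the tables. Section 3.3 allows interim doses in consultation with the SRC. Core Section 9.2 allows an alternative schema when ongoing safety review supports an intermediate dose. Core Section 9.6 and Appendix E let the SRC recommend changes. Sections 3.8 and 3.10 allow lower starting doses on emerging data. A sensible sponsor would find a way down. This stands: the sentence is not an absolute bar, and it does not order a third subject to be enrolled. But none of these provisions expressly waives a rule worded as mandatory. The Figure 7 footnote concerns ending the study, and only at the first dose level.

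**Convention.** Part A's 3+3 rules (Table 6) also act at 2 of 3 and have no row for 2 of 2. The third result has some use, since in Figure 6 it separates D from DU. And 2/6 is S in Figure 6, so four further subjects without events could change the answer. This also stands in part, but at three evaluable subjects the table says D, so following it means leaving before six are reached.

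**Stronger readings the documents do not support.** A reader might infer that two events in two subjects show the dose to be too toxic. With a Beta(1,1) prior, P(rate > 30%) is 97.3%. But E1 starts at 7 mg/kg, where Section 1.3.4.1 reports no DLTs among nine monotherapy subjects. Borrowing that record in full, as 0/9 evaluable (an assumption), gives Beta(3,10) and only 25.3%. The point rests on the printed cells, not on such probabilities. A reader might also take the SAP wording as a contradiction. It describes an older C1 that only escalated (6, 8, then 10 mg/kg), so it is not an error.

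**Conclusion.** The point holds in narrow form. When both of the first two evaluable subjects have events counted against the same table, the mandatory minimum conflicts with that table, and the text gives no express exception. It should not be read as forbidding every move down, or as requiring a third subject to be dosed.

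The consequence is small. The state is uncommon, and its frequency cannot be estimated reliably from one non-evaluable subject in six. No enrolled subject is shown to have been affected: the C1 decision at 6 mg/kg rested on 2 of 5 evaluable subjects, which Figure 6 prints as D. The SAP (Sections 1 and 8) reports enrollment only in Parts A, A2, B and C1, and enrollment has stopped. The value lies in any reopening or reuse of this wording.

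The conclusion assumes that DLTs are read in Figure 6 and delayed events in Figure 7, as the two targets imply. Severity is minor. Confidence in the table logic is high.

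**What to change.** Keep the three-subject minimum and add to Sections 3.6, 3.8 and 3.10, and to the matching text in Section 3.1 and the synopsis:

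*Except that, if both of the first 2 evaluable subjects at a dose level have events counted against the same decision table, accrual at that level stops and de-escalation may proceed without a third evaluable subject. After a single event in 1 or 2 subjects, the cohort of 3 is completed.*

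The limit to the first two evaluable subjects matters because Figure 6 prints S at 2/6. Restricting the minimum to escalation alone would go too far: both tables print D at 1/1 and 1/2, so one event could then move the cohort down.

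The cost is one sentence in five places, with no added subjects or data. The downside is that a dose may occasionally be left one subject earlier. In Figure 6 it would also stay formally open (D) where a third event would have closed it (DU). The predicted chance of that third event is 3/4 = 75% with Beta(1,1), and 3/13 = 23% for E1 with full borrowing of 0/9.

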The mTPI-2 cohort will evaluate up to 5 dose levels based on DLT events and TRAEs leading to treatment delay or discontinuation, including events of special interest (eg, ocular toxicity and peripheral neuropathy). As events of special interest have been observed at later time points, TRAEs leading to treatment interruption (ie, missed dose) or treatment discontinuation will be evaluated over an extended interval that encompasses the first 3 infusions (42 days). An event for the mTPI-2 cohort is defined as either a DLT or a TRAE leading to treatment interruption (ie, missed dose) or treatment discontinuation. The decision-making tables for the mTPI-2 cohort are provided in [Appendix C](#).

For dosing, AIBW should be applied ([Appendix F](#)).

Subjects may be permitted individual dose escalations to previously cleared dose levels following consultation with the Medical Monitor.

The DLT assessment period for dose escalation is 21 days.

Subjects in Part A who discontinue study drug administration for reasons other than DLTs may be replaced to ensure the minimum number of subjects required for DLT evaluation is enrolled.

As of November 2019, the RP2D for CX-2009 administered every 21 days was determined to be 7 mg/kg. For justification of this dose, refer to Sections [1.3.4.1](#) and [5.2](#).

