Part E1 is only open to those countries in which the Health Authority permits the combination of CX-2009 and CX-072 to be investigated. The dose of CX-072 will be fixed at the RP2D (1200 mg every 21 days). The starting dose of CX-2009 will be 7 mg/kg (the every 21-day monotherapy RP2D as determined in Parts A/A2). Lower starting doses may be used based on emerging data and in consultation with the SRC. The mTPI-2 design will be used to determine the MTD/RP2D for this schedule. The following cohort's dose will be increased or decreased according to the defined dose escalation rules based upon the observed safety tolerability profile as determined in consultation with the SRC. Prior to a dose escalation/de-escalation, a minimum of 3 evaluable subjects must be assessed per the mTPI-2 algorithm ([Figure 6](#)). Part E1 will enroll subjects in 1 or more of the tumor types listed in [Table 4](#). The tumor types have been selected for their responsiveness to MTIs and general availability of lesion safe to be biopsied.

Part E1 will evaluate dose levels based on DLT events and TRAEs leading to treatment delay or discontinuation, including events of special interest (eg, ocular toxicity and peripheral neuropathy).

AEs that meet DLT criteria (within the 21-day DLT period) and delayed AEs that lead to treatment interruption/discontinuation within the first 6 weeks, thus encompassing the first 3 doses (DLT rate $\leq 30.0\%$; delayed AE rate $\leq 20.0\%$), will be monitored. Decision for dose escalation/de-escalation will be made by the Sponsor in consultation with the SRC guided by the decision-making table ([Appendix C](#)). The selection of MTD/RP2D will be based predominantly on safety and may take other factors into account such as PK/PD and clinical activity.

Subjects who discontinue study drug administration for reasons other than DLTs may be replaced to ensure the minimum number of subjects required for DLT evaluation is enrolled.

**3.11 Part E2 (CX-2009 + CX-072):
Dose Expansion for Every 21-Day Dosing Regimen in Selected Tumor Types
(Maximum n ≤ 200)**

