5.5.4 Treatment Delays, Dose Modification, and Missed Doses

Treatment or visit delays for public holidays, weather conditions, or other unforeseeable circumstances (including toxicity considered unrelated to study treatment) do not constitute a protocol violation. However, delayed visits should be completed at the first available opportunity.

There must be a minimum of 21 days (Parts A, A2, B, E1, and E2) or 14 days (Parts C1, C2, D1, and D2) between study drug infusions (a window of ± 2 days may occur). In exceptional circumstances, an infusion may be delayed for up to 7 days. Infusions that cannot be administered in that timeframe will be considered a missed dose, and the subject's next planned dose should be 42 days (every 21-day dosing regimen; Parts A, A2, B, E1, and E2) or 28 days (every 14-day dosing regimen; Parts C1, C2, D1, and D2) after the last administered dose. A subject will be considered to have experienced a prolonged treatment delay and study drug will be discontinued if the subject misses 2 consecutive infusions, except as provided for in Section 5.5.4.1 and Section 5.5.4.2.

Subjects benefitting from treatment may be allowed longer treatment delays after discussion with the Medical Monitor. Subjects should be assessed for resolution of toxicity (eg, by scheduled physical examination, laboratory testing, etc.) at a frequency deemed by the Investigator to be appropriate for the specific clinical situation.

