		Cycle 1 DLT Assessment Day 1 to Day 21				Cycle 2			Cycle 3 & On ²³			EOT ²⁴	
Study/Visit Day ¹	-30 to 0	1	4 (±1d)	8 (±2d)	15 (±2d)	1 (±2d)	8 (±2d)	15 (±2d)	1 (±2d)	8 (±2d)	15 (±2d)	(±7d)	Refer to footnote
Complete ophthalmology examination ¹²	X	All subjects within 5 days prior to Cycle 1, Day 1; Cycle 2, Day 1; Cycle 3, Day 1; and at the EOT Visit. Subjects who report treatment-emergent changes in vision or other ocular symptoms will undergo repeat examinations prior to infusion every other cycle and as clinically indicated.											
Ocular symptom assessment ¹³	X	X				X			X			X	
Vital signs		Refer to Table 17											
ECOG performance status ¹⁴	X	X				X			X			X	
Hematology ¹⁵	X	X		X	X	X	X	X	X	X	X	X	
Serum chemistry ^{16,17}	X	X		X	X	X	X	X	X	X	X	X	
Coagulation ¹⁸	X	As clinically indicated											X
Urinalysis ¹⁹	X											X	
Pregnancy test ²⁰	X	X				X			X			X	X
Archival/baseline tumor biopsy	X												
Tumor markers ²¹		As clinically indicated											
Biopsy (fixed and frozen) and plasma biomarker sample ²²						X (3 to 5 days after C2D1)							
Plasma PK and ADA		Refer to Table 24 (Part E1) and Table 25 (Part E2)											

Table 16. Schedule of Procedures: Parts E1 and E2

Note: For Parts E1 and E2, each cycle constitutes 21 days.

1. Study visits that cannot occur on the scheduled day due to unforeseen circumstances other than toxicity (eg, weather or holidays) should be completed as close to the scheduled date as possible. Laboratory assessments may be performed up to 2 days prior to the visit or as otherwise specified in the Schedule of Procedures. Visits conducted outside the windows are to be discussed with the Medical Monitor or designee in advance.
2. Medical history to include confirmation of previous cancer diagnosis, and record cancer treatment history, current symptoms at baseline, and current medications, as well as those taken within 30 days of first dose of study drug. An ophthalmology history is also required.
3. AEs will be assessed and reviewed prior to infusion and at any other visit that includes a physical examination.

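### Part E1's six-week delayed-AE window ends as dose 3 falls due (Day 43), so it gives little or no follow-up after the third dose that it is said to cover

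*Protocol*

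**What the plan says.** Sections 3.6 (Part C1), 3.8 (Part D1) and 3.10 (Part E1), with the matching synopsis text, share one monitoring sentence. Besides DLTs, dose decisions look at "delayed AEs that lead to treatment interruption/discontinuation within the first 6 weeks, thus encompassing the first 3 doses", with a limit of 20% for the delayed-AE rate. C1 and D1 dose every 14 days and E1 every 21 days. The DLT period in the same sentence does follow the schedule (28 days in C1 and D1, 21 days in E1); the six weeks do not.

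Section 3.2 (Part A, also every 21 days) gives the reason for the longer window: "As events of special interest have been observed at later time points". It says that treatment-related AEs leading to interruption or discontinuation "will be evaluated over an extended interval that encompasses the first 3 infusions (42 days". It also supplies the event definition: "An event for the mTPI-2 cohort is defined as either a DLT or a TRAE leading to treatment interruption (ie, missed dose", or to discontinuation. Section 3.10 does not repeat that definition. It speaks of treatment-related AEs that lead to delay or discontinuation.

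On timing, section 5.5.4 sets the gap between infusions: "There must be a minimum of 21 days (Parts A, A2, B, E1, and E2) or 14 days (Parts C1, C2, D1, and D2", with a window of 2 days either way. It adds: "In exceptional circumstances, an infusion may be delayed for up to 7 days". After that, "Infusions that cannot be administered in that timeframe will be considered a missed dose". Appendix B, Table 16, states: "For Parts E1 and E2, each cycle constitutes 21 days".

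**The concern.** The window exists to catch toxicity, chiefly ocular toxicity and neuropathy, that builds up after the DLT period, and the text says that it does so over three doses. On an every-21-day schedule, six weeks is two full cycles, so the third dose falls due as the window closes.

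Two things would be at stake. First, those who apply the 20% limit in E1 could believe that they have seen tolerability through dose 3 when they have seen it through dose 2. Second, the synopsis section on sample size lets the combination expansion use either schedule in the light of the D1 and E1 data. The delayed-AE rates of those two parts would then be read against one limit while resting on different numbers of doses.

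**Working it through.** **Inputs.** Dosing interval: 14 days in C1 and D1, 21 days in E1 (5.5.4; Table 16). Permitted delay before a dose counts as missed: 7 days (5.5.4). Window: six weeks (3.6, 3.8, 3.10). Day count: Table 16 labels the 21-day DLT period as Day 1 to Day 21, so by the same count six weeks is Day 1 to Day 42.

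**Formulas.** Due day of dose k = 1 + (k − 1) × interval. A dose is missed after its due day + 7.

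| | Every 14 days (C1, D1) | Every 21 days (E1) |
|---|---|---|
| Dose 2 due | 1 + 14 = Day 15 | 1 + 21 = Day 22 |
| Dose 3 due | 1 + 28 = Day 29 | 1 + 42 = Day 43 |
| Dose 4 due | 1 + 42 = Day 43 | 1 + 63 = Day 64 |
| Doses due by Day 42 | 3 | 2 |
| Doses due by Day 43 | 4 | 3 |
| Dose 2 missed after | 15 + 7 = Day 22 | 22 + 7 = Day 29 |
| Dose 3 missed after | 29 + 7 = Day 36 | 43 + 7 = Day 50 |
| Days from dose 3 to Day 42, dosing day included | 14 | 0 |

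**The plan's own figure.** Three doses in six weeks is reproduced for C1 and D1 with the window ending on Day 42. For E1 it is reproduced only if Day 43 is counted as inside the window. Dose 3 then sits on the last day, with no follow-up beyond it.

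**Effect of the 2-day dosing window.** Earliest every-21-day dosing is Days 1, 20 and 39. Dose 3 is then inside the window with a few days of follow-up, but it is missed only after 39 + 7 = Day 46, still outside. Latest every-14-day dosing is Days 1, 17 and 33, with dose 3 missed after 33 + 7 = Day 40, still inside.

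**Three readings of the E1 event.**

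- *Missed dose (the section 3.2 meaning).* Within six weeks, E1 can register dose 2 as missed but not dose 3. C1 and D1 can register both.
- *Delay (the section 3.10 wording).* A late dose 3 can be noted without waiting 7 days, but in general not before it is due on Day 43.
- *AE dated by onset.* E1 covers toxicity after dose 1 (Days 1–21) and dose 2 (Days 22–42). C1 and D1 also cover toxicity after dose 3 (Days 29–42).

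A discontinuation before Day 43 is captured on every reading.

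**Illustration only, missed-dose reading.** Assume a constant, independent chance p per dose of a toxicity-related miss; the documents give no p. The share of subjects with an event is p if only dose 2 can register, and 1 − (1 − p)² if doses 2 and 3 can. For p = 5%, 10%, 15% and 20% this gives 5.0% against 9.8%, 10.0% against 19.0%, 15.0% against 27.8%, and 20.0% against 36.0%.

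**The case against.** The strongest reply has four parts.

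1. *The sentence can be true for both schedules.* Counted as elapsed time, six weeks ends on Day 43; E1 then contains three doses and C1 and D1 four, and a window of four still encompasses the first three. This stands. A reader might infer that the sentence is impossible for one schedule or the other, but that depends on a day-count convention the protocol does not fix. What this reply cannot supply is follow-up after dose 3.

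2. *The missed-dose definition belongs to Part A.* Section 3.10 refers to delay. Moreover, Table 16 places an ophthalmology examination within 5 days before Cycle 3 Day 1 (Days 38–42), so an ocular reason to hold dose 3 could be found inside the window. This also stands, and Day 50 is therefore the result of one reading. However, such a finding reflects toxicity after dose 2; it says nothing about tolerability after dose 3.

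3. *A common calendar window is defensible.* Two 21-day cycles and three 14-day intervals both span 42 days. At 7 mg/kg in E1 and 4 mg/kg, the next planned C1 dose, the cumulative doses before Day 43 are 2 × 7 = 14 and 3 × 4 = 12 mg/kg. The expansion stopping rule in section 9 uses six weeks on both schedules without a dose count. This is a fair case for six weeks, but not for describing them as covering three doses.

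4. *Late toxicity would be seen anyway.* The SRC and DSMB review accumulating safety data, and section 8.7 requires report within 24 hours of eye disorders of Grade 3 or higher and of Grade 2 neurotoxicity. True. The gap lies in what the 20% rule counts, not in what the sponsor would know.

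**Conclusion.** The point holds and is minor. For Part E1, the six-week window ends as dose 3 falls due. It gives no follow-up after dose 3 on nominal dosing and only a few days at best. Against C1 and D1 the rule is one dose short, whether it counts missed doses (dose 2 only, against doses 2 and 3) or AEs by onset (toxicity after two doses, against three). This rests on calendar arithmetic from the stated intervals. The Day 50 figure also assumes that an interruption is a missed dose, as in section 3.2.

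Two stronger conclusions that a reader might draw are not supported.

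- *That E1 would understate event rates by a known amount, for example 20% for a true 36%.* Those percentages need the missed-dose reading and an assumed p. If AEs are dated by onset, toxicity after dose 2 that causes dose 3 to be held is counted, and the contrast falls away. A constant p also sits poorly with toxicities that are said to appear late.
- *That a dose decision was compromised.* Appendix C guides the sponsor and SRC and does not bind them. Part A carries the same wording but is closed, and section 5.2.1.2 rests the 7 mg/kg choice on observed clinical data, notably ocular toxicity, and on PK simulations. SAP section 4.2 places all 99 treated subjects in Part A, A2, the mTPI-2 cohort, B and C1 (37 + 39 + 10 + 3 + 10 = 99). No E1 decision is shown to be affected.

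**What to change.** Choose one of two edits in section 3.10 and the E1 synopsis; C1 and D1 can keep six weeks.

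- *Define the event by dose.* Count a treatment-related AE that leads to discontinuation, or to dose 2 or dose 3 being missed, meaning not given within 7 days of its due date, and assess it through Day 50. If dose 2 was given late within its 7-day allowance, the due date of dose 3 moves with it; the text should say so. For subjects dosed on schedule, the read-out moves from Day 42 to Day 50, which is 50 − 42 = 8 days per cohort. The 21-day DLT period is unchanged. Infusion dates are already recorded (5.5.7), so no new data are needed.
- *Restate the coverage.* Keep six weeks, delete the clause about the first three doses, and state that in E1 the rule covers toxicity after the first two doses. This costs nothing but the edit.

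Enrollment has stopped, so if E1 is not reopened the practical step is to correct the sentence before it is reused, and to avoid describing an every-21-day six-week window as three-dose coverage in reporting.
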